3.4.3 Exploratory Biomarker Analysis

As part of the exploratory analysis, cT1 will be analyzed as described for MRI-PDFF above.

Lipodomics data will be available for a sub-set of the patients; data will be analyzed using similar ANCOVA or MMRM models as described for the secondary endponts.

The AI Histology data will be compared with the liver biopsy results from the manual reads.

3.5 Pharmacokinetic Assessment

3.5.1 Sample Collections for Pharmacokinetic Analysis

For the Trough PK Population, PK blood samples of NST-4016 will be collected pre-dose at Visit 2 through to Visit 9 (or the ET Visit, if applicable).

For the Intensive PK Population, PK blood samples of NST-4016 will be collected at the following timepoints, in relation to the first dose of study drug on Visit 2: pre-dose (within 1 hour prior to first

dose), followed by 1, 2, 3, 4, 6, and 8 hours (+/- 10 minutes) post-dose (Day 0) and at 24hours post-dose (+/- 1 hour, but prior to the second dose of study drug on Day 1).

3.5.2 Handling Missing or Below the Lower Limit of Quantification Data

For PK concentration data, if the actual sampling time is missing, but a valid concentration value has been measured, the concentration value will be flagged, and the scheduled time point may be used for the calculation of PK parameters.

In cases of missing pre-dose concentrations for Visit 2 the missing components may be assumed as zero. For all other cases, the missing data will not be imputed.

At Visit 2, PK blood concentration values that are below the lower limit of quantification will be presented as "BLQ" in the concentration data listing.

For the individual concentration and PK parameter calculation, the following rules will be applied:

- If one or more BLQ values occur before the first measurable concentration, they will be assigned a value of zero.
- If BLQ values occur between measurable concentrations in a profile, the BLQ should be omitted (set to missing).
- If BLQ values occur after the last measurable concentration in a profile, the BLQ should be omitted (set to missing).
- For the concentration summary and mean plot preparation, the following rules will be applied: Mean concentration at any individual time point will only be calculated if at least half of the subjects have valid values (i.e. quantifiable and not missing) at this time point
- In cases where a mean value is not calculated due to the above criterion not being met, the value will be set to missing
- BLQ values will be set to zero

3.5.3 Pharmacokinetic Concentration

For the Trough PK Population, trough plasma PK concentrations, defined as the plasma PK concentration taken prior to the administration of study drug, at Visits 3 to 9 will be listed and summarized descriptively by visit and treatment. Mean (+/- SD) trough plasma PK concentrations will be plotted by visit and treatment group on a linear and semi-logarithmic scale against nominal sampling time points. Individual trough plasma PK concentrations will be plotted on linear and semi-logarithmic scales against actual sampling time points relative to dosing time.

For the Intensive PK Population, Individual plasma PK concentrations will be listed and summarized by treatment group at each nominal time point descriptively. Mean (+/- SD) plasma PK concentrations will be plotted by treatment group on linear and semi-logarithmic scales against nominal time. Individual plasma PK concentrations will be plotted on linear and semi-logarithmic scales by treatment group against actual sampling time points relative to dosing time.

For all plots, LLOQ will be plotted as a reference line.

3.5.4 Pharmacokinetic Parameters

For the Intensive PK Population at Visit 2, the following plasma PK parameters of NST-4016 will be determined using non-compartmental methods as appropriate:

Parameter	Description
C _{max}	Maximum observed plasma concentration; determined directly from the concentration time profile; if the maximum plasma concentration occurs at more than one time point, C_{max} is defined as the first maximum value
T _{max}	Time to C_{max} ; If the maximum value occurs at more than one time point, T_{max} is defined as the first time point with this value.
λz	Apparent first-order terminal elimination rate constant calculated from a semi-log plot of the plasma concentration versus time curve. The parameter will be calculated by linear least-squares regression analysis using points in the terminal log-linear phase.
t _{1/2}	Apparent first-order terminal elimination half-life; calculated as $ln(2)/\lambda z$
AUC _{0-t}	Area under the plasma concentration-time curve from time 0 to the time of the last observed concentration
AUC _{0-inf}	Area under the plasma concentration-time curve from time 0 extrapolated to infinity; calculated as (AUC0-last+ Clast/ λz)
AUC _{%extrap}	Percent of AUC0-infextrapolated, represented as (1 -AUC0-t/AUC0- inf)*100
CL/F	Apparent total plasma clearance after oral administration; calculated as Dose/AUC0-inf
Vz/F	Apparent volume of distribution during terminal elimination phase after oral administration; calculated as Dose/[λz^*AUC0 -inf]

Actual collection times will be used for the calculation of PK parameters. AUCs will be calculated using linear up log down method.

 λz will not be presented for subjects who do not exhibit a terminal elimination phase in their concentration-time profiles. In order to estimate λz , linear regression of concentration in logarithm scale versus time will be performed using at least 3 data points. Uniform weighting will be selected to perform the regression analysis.

The constant λz will not be assigned if one of the following occurs:

1. The terminal elimination phase is not linear (as it appears on a semi-logarithmic scale).

- 2. The terminal elimination rate constant indicates a positive slope ($\lambda z > 0$).
- 3. Tmax is one of the three last data points.

NorthSea Therapeutics B.V.	CONFIDENTIAL	Statistical Analysis Plan
Protocol NST-02		Version 1.0, 14 February 2023

The constant λz and its derived parameters will be listed but excluded from statistical analysis if one of the following occurs:

- 1. The adjusted regression coefficient (R^2) is less than 0.8.
- 2. The AUC%extrap exceeds 20%.

If λz is not assigned, the values of any associated PK parameters (e.g. AUC_{0-inf}, AUC_{%extrap}, t_{1/2}, CL/F, or V_z/F) will not be calculated.

No PK parameters will be calculated for subjects with 2 or fewer detectable concentrations in their PK profile.

Plasma PK parameters will be summarized by treatment using descriptive statistics for the Intensive PK Population.

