Study drug dosing will begin at Visit 2 (Week 0, Day 0) and will continue daily for 52 weeks. During the 52-week treatment period, patients will return to the clinic for study visits every 1 to 3 months. The following assessments will occur at every study visit during the treatment period: adverse events, concomitant medications, body weight, vital signs, physical examinations, laboratory evaluations (hematology, biochemistry, coagulation, and lipid panels and urinalysis), and trough PK sampling. For a subset of patients (approximately 8 patients per group) at pre-identified sites, blood samples for analysis of additional PK parameters will also be collected predose and up to 24 hours postdose at Visit 2. In addition, hepatic imaging will be performed at Visit 5 (after 16 weeks of treatment) and Visit 9 (after 52 weeks of treatment).

Evaluation of liver inflammation and fibrosis biomarkers (Homeostatic Model Assessment for Insulin Resistance [HOMA-IR], hsCRP, Pro-C3, and ELF panel) will be performed at Visits 2, 5, and 9. Twelve-lead ECGs will be performed at Visits 2, 5, 7, and 9, and a liver biopsy will also be performed at Visit 9. Throughout the study, patients will be monitored for suspected drug-induced liver injury.

A Safety Follow-up Visit (Visit 10) will occur 14 days after the last dose of study drug to assess adverse events, concomitant medications, body weight, vital signs, physical examination findings, laboratory parameters, and 12-lead ECGs. Lipid parameters will be monitored throughout the follow-up period and will be managed by the Investigator.

Patients who discontinue early from the study for any reason prior to completion of the treatment period will be requested to return to the clinic for an Early Termination (ET) Visit as soon as possible after their last intake of study drug. Patients who discontinue early from the study for any reason after completion of the treatment period and before the Safety Follow-up Visit will be requested to return to the clinic for an ET Visit as soon as possible and no later than the planned Safety Follow-up Visit.

From screening through follow-up, the total study duration for each patient who completes the entire treatment period will be approximately 62 weeks. For a summary of procedures to be performed at each visit, refer to the Schedule of Procedures in Appendix A.

An external, independent DSMC will review all available unblinded preliminary safety and biomarker results per the DSMC Charter.

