#### 9.2.1.6 Pharmacokinetic analysis

Trough plasma PK concentrations at Visits 3 to 9 will be summarized descriptively by visit for the Trough PK Population.

For the subset of patients with intensive PK sampling data, additional PK parameters will be summarized by treatment using descriptive statistics for the Intensive PK Population. No formal statistical analysis of PK parameters will be performed.

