2.3.5 Pharmacokinetic Parameters

The following PK parameters will be summarized:

• NST-4016 concentrations (all patients)

In addition, for the Intensive PK subset:

- AUC_{0-t}
- AUC_{0-inf}
- CL/F
- C_{max}
- T_{max}
- V_z/F

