7 PROGRAMMING SPECIFICATIONS

Analyses will be performed using SAS[®] version 9.4 or higher. All available data will be presented in patient data listings which will be sorted by patient and visit date as applicable.

Phoenix WinNonlin version 8.3 or higher will be used to calculate PK parameter estimates. PK parameter estimates will also be calculated via SAS and verified with the Phoenix WinNonlin results.

Detailed Programming Specifications will be provided in a separate document(s).

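### SAP 3.5.4: the sign in the second λz rejection rule contradicts the section's own formulas and, applied as written, would block AUC0-inf, CL/F and Vz/F

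*SAP*

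**What the plan says.** The parameter table in SAP 3.5.4 defines λz as the apparent first-order terminal elimination rate constant, obtained by log-linear regression of the terminal points. Other parameters are built on it:

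- t1/2, described as "Apparent first-order terminal elimination half-life; calculated as" ln(2)/λz
- AUC0-inf = AUC0-last + Clast/λz
- AUC%extrap = (1 − AUC0-t/AUC0-inf) × 100
- CL/F = Dose/AUC0-inf
- Vz/F = Dose/(λz × AUC0-inf)

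The text below the table says that λz "will not be presented for subjects who do not exhibit a terminal elimination phase in their concentration-time profiles". It then gives three conditions, any one of which leaves λz unassigned. The second is "The terminal elimination rate constant indicates a positive slope", followed by the bracket λz > 0. The section later states that if λz "is not assigned, the values of any associated PK parameters" will not be calculated, and it names AUC0-inf, AUC%extrap, t1/2, CL/F and Vz/F as examples.

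SAP 2.3.5 ("In addition, for the Intensive PK subset") and Protocol 8.14 list the same six parameters: AUC0-t, AUC0-inf, CL/F, Cmax, Tmax and Vz/F.

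**The concern.** The bracket states the condition for a valid elimination phase and uses it as a ground for rejection. A programmer who codes it as written discards λz for every patient whose concentrations fall, and with it half of the listed intensive-PK parameters. The bracket would also let through a negative λz from a rising terminal phase, which is what the rule is meant to stop, unless another condition caught it.

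The stake is limited to the pharmacokinetic description. SAP 2.1.2 makes characterising the PK a secondary objective, but no efficacy, safety or dose conclusion in either document rests on these parameters.

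**Working it through.** **1. Sign required by the formulas.** For declining concentrations the regression of ln(C) on time has a negative slope. A rate constant that gives a positive half-life from ln(2)/λz must be λz = −slope, which is above zero. The same sign is needed for AUC0-inf to exceed AUC0-t and for Vz/F to be positive. Rule 2 rejects λz > 0. The two conflict.

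**2. Could the bracket mean the raw slope?** If λz = slope, rule 2 agrees with its own words, but every formula in step 1 then takes a negative λz.

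**3. Numerical illustration.** The documents give no PK values for NST-4016, so all PK inputs here are assumed and serve only to show signs: one-compartment oral model, dose 600, V/F 50, absorption rate ka and elimination rate ke as tabulated (per h). Sampling times are those of Protocol 8.14 (0, 1, 2, 3, 4, 6, 8, 24 h). The slope comes from ln(C) at the last three points, and AUC from the SAP's linear-up log-down method.

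*With λz = −slope:*

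| ka | ke | Slope | λz | t1/2 (h) | AUC0-t | AUC0-inf | AUC%extrap | CL/F | Vz/F |
|---|---|---|---|---|---|---|---|---|---|
| 1.0 | 0.05 | −0.0499 | 0.0499 | 13.9 | 162.8 | 239.1 | 31.9 | 2.51 | 50.3 |
| 1.0 | 0.10 | −0.0998 | 0.0998 | 6.9 | 106.8 | 118.9 | 10.2 | 5.05 | 50.5 |
| 1.0 | 0.20 | −0.1997 | 0.1997 | 3.5 | 58.2 | 58.8 | 1.1 | 10.20 | 51.1 |
| 1.5 | 0.30 | −0.3000 | 0.3000 | 2.3 | 38.3 | 38.4 | 0.1 | 15.63 | 52.1 |

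Tmax falls at 1 to 3 h, so the third condition (Tmax among the last three points) is not triggered. The bracket λz > 0 rejects 4 of 4 profiles. The words about a positive slope reject 0 of 4. Cmax, Tmax and AUC0-t are available in all four whichever reading is used.

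*With λz = slope, for ke = 0.10:*

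- t1/2 = ln(2)/(−0.0998) = −6.9 h
- The extrapolated term is 118.9 − 106.8 = 12.1 in size and now enters with a minus sign, so AUC0-inf = 106.8 − 12.1 = 94.7, below AUC0-t
- AUC%extrap = (1 − 106.8/94.7) × 100 = −12.8%
- Vz/F = 600/(−0.0998 × 94.7) = −63.5

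Half-life, AUC%extrap and Vz/F are negative in the other three profiles too. No single sign convention satisfies both the rule and the formulas.

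**4. Reach.** Of the six parameters in SAP 2.3.5, three use λz directly or through AUC0-inf (AUC0-inf, CL/F, Vz/F) and three do not (Cmax, Tmax, AUC0-t). t1/2 and AUC%extrap are also lost, but they appear only in the 3.5.4 table. Protocol 3.1 describes the sampling as "For a subset of patients (approximately 8 patients per group) at pre-identified sites". With two active groups that is about 2 × 8 = 16 patients.

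**5. Not every blocked value would have been summarised.** SAP 3.5.4 separately lists, but excludes from statistical analysis, λz and its derived parameters when AUC%extrap exceeds 20%. The first profile (31.9%) would be excluded on that ground under the intended rule as well. In this model the 20% limit is reached at a half-life of 9.6 to 10.0 h for absorption rates of 0.6 to 1.5 per h.

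**The case against.** The strongest reply is that nobody would run the rule this way. The words beside the bracket speak of a positive slope, a neighbouring sentence withholds λz only where there is no elimination phase, and a rule that removes parameters the same table orders to be determined is not a plausible intention. The bracket may be loose shorthand for the regression slope. This stands as a statement of intent, and it is why the point is minor. It does not make the text consistent, because the shorthand reading breaks the formulas (step 3).

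A second reply is that an inequality sign can be corrupted when a document is converted. That is possible but not shown: the bracket is legible and sits directly beside the words it restates. Checking it against the signed SAP takes a moment.

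A third reply is that the consequence is negligible. Protocol 9.2.1.6 says "No formal statistical analysis of PK parameters will be performed", and SAP 7 adds a cross-check: "PK parameter estimates will also be calculated via SAS and verified with the Phoenix WinNonlin results". The low impact is granted. The cross-check would probably expose a literal implementation in one system, but two programs that both followed the bracket would agree with each other. SAP 7 also leaves programming detail to separate documents that are not available here, so they cannot be relied on to correct the rule.

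**Conclusion.** The concern holds. Rule 2 carries a sign error that contradicts the formulas in its own section under either sign convention, and neither document corrects it. Followed as written, it removes three of the six listed intensive-PK parameters for every declining profile in about 16 patients on active treatment, and leaves the other three and all trough results intact. The contradiction is algebraic and does not depend on the assumed PK values; those affect only the illustrative magnitudes and the remark on the 20% limit. It is a correction to consider, not a threat to the trial's conclusions.

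**What to change.** Replace the second condition in SAP 3.5.4 with: the slope of the terminal log-concentration regression is zero or positive (λz ≤ 0). Zero belongs in the rejected set because the formulas divide by λz. Put the same condition in the programming specifications referred to in SAP 7, so that the SAS and WinNonlin calculations use one rule. The cost is a one-line text change, with no extra data or analysis.

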3.6 Safety Assessment

Safety data include AEs, vital signs, physical examinations, ECGs and clinical laboratory parameters and will be summarized by actual treatment received based on the Safety Population.

3.6.1 Adverse Events (AEs)

An adverse event is defined as any untoward medical occurrence in a clinical investigation patient administered a pharmaceutical product, which does not necessarily have a causal relationship with this treatment. An adverse event can therefore be any unfavorable and/or unintended sign (including an abnormal laboratory finding), symptom, or disease temporally associated with the use of an investigational medicinal product, whether or not related to the investigational medicinal product. A treatment emergent AE (TEAE) is defined as a new or worsening adverse event after the first dose of study drug.

All AEs will be coded to system organ class and preferred term using MedDRA version 22.0.

An overview of AEs will be provided including counts and percentages of patients and number of events by treatment group and overall for Safety Population (and event counts) with the following:

- Any Adverse Event
- Any TEAEs
- Maximum severity of TEAEs
- Study drug related TEAEs
- Maximum severity of study drug related TEAEs
- TEAEs leading to discontinuation of study drug
- Any TEAEs of special interest (TEAESI)
- Any serious TEAEs (TESAEs)
- Study drug related TESAEs
- TESAE/TEAESIs leading to discontinuation of study

- TESAEs leading to death
- TESAEs related to COVID leading to death

The TEAEs described above will be summarized separately by System Organ Class and Preferred Term (and by maximum severity).

Listings will be presented specifically for all TEAEs, TEAESI, TESAEs, TEAEs Leading to Discontinuation of Study Drug, TEAEs Leading to Discontinuation of Study and TESAEs Leading to Death.

3.6.2 Clinical Laboratory Tests

Fasting Hematology, biochemistry, coagulation and lipid panels and urinalysis will be collected at all study visits. A list of laboratory tests to be performed is included in Protocol Appendix B.

Descriptive statistics of each clinical laboratory parameter will be presented for baseline values and for values and the change and percent change from the baseline at each post-baseline visit by treatment group and overall.

Values outside the normal range will be categorized as High (i.e., above the normal range) or Low (i.e., below the normal range) based on the central laboratory's normal reference range. The number and percentage of patients with values outside the normal range will be summarized by parameter for baseline and for each post-baseline visit.

Shift tables will also be presented for baseline versus maximum-baseline values and baseline versus minimum post-baseline values.

All safety laboratory data will be presented in patient listings.

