### 1.4.1.2 Clinical pharmacodynamics

Rapid, sustained, and significant dose-dependent decreases were seen in alanine aminotransferase (ALT), aspartate aminotransferase (AST), gamma glutamyl transferase (GGT), and alkaline phosphatase (ALP) at levels predictive of histologic improvement (see Table 1). Both doses showed significant reductions in N-terminal type 3 collagen propeptide (Pro-C3) and enhanced liver fibrosis (ELF) score (both total score and individual components) supporting an effect on fibrogenesis. High -sensitivity C-reactive protein (hsCRP) significantly decreased by 52% with 600 mg, in conjunction with improvements in glycemic control and key atherogenic lipoproteins. There were no changes in weight or body mass index (BMI), suggesting a treatment effect independent of weight loss. Liver fat content was unchanged with both doses, consistent with the icosabutate mechanism of action.

 Table 1.
 Placebo-Adjusted Absolute Changes in Non-Invasive Biomarkers

Biomarker (Unit)	Icosabutate 300 mg (n=33)	Icosabutate 600 mg (n=35)
ALT (U/L)	-19*	-25.4*
AST (U/L)	-9.4#	-13.5#
GGT (U/L)	-16.9#	-28.6*
ALP (U/L)	-12.7*	-19.6*

Table 1. Placebo-Adjusted Absolute Changes in Non-Invasive Biomarkers (Continued)

Biomarker (Unit)	Icosabutate 300 mg (n=33)	Icosabutate 600 mg (n=35)
Bilirubin (mg/dL)	-0.0	-0.14#
Pro-C3 (ng/mL)	-4.5*	-4.6*
ELF	-0.4#	-0.6*
hsCRP (mg/L)	-1.2	-2.3#
HbA1c (%)	0.0	-0.3
HOMA-IR	-1.5	-2.1
LDL-C (mg/dL)	5.5	-3.9
HDL-C (mg/dL)	3.2#	2.3
Remnant-C (mg/dL)	-6.1#	-8.0*
ApoC3 (mg/dL)	-1.6#	-2.7*
TG (mg/dL)	-27.1#	-34.0#

\* = p < 0.001, # = p < 0.05

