## 5.2 Rationale for Dosing

The maximum dose selected for this study (600 mg) was previously administered for 12 weeks daily in patients with hypertriglyceridemia or mixed dyslipidemia and demonstrated statistically significant and clinically meaningful reductions in triglycerides and cholesterol and was shown to be safe and well tolerated. Single ascending doses >600 mg (up to 2800 mg) resulted in increasing gastrointestinal side effects, which were mainly mild. The low dose selected for this study (300 mg) demonstrated significant reductions in triglycerides and cholesterol, although not as notable as the effects seen with 600 mg dosing. These 2 doses are expected to provide evidence of a dose-response relationship in patients with NASH. Once-daily dosing is consistent with the sustained PD effects seen on lipids in repeat-dose studies.

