#### 5.6.2 Restricted Medications and/or Procedures

Patients receiving lipid-lowering treatments need to be on stable therapy for at least 3 months prior to screening and must agree to remain on a stable regimen for their entire participation in the study unless the patient is unable to achieve adequate control with current therapy. Patients may switch drugs within a class prior to screening if the lipids remain controlled (as assessed 30 days after the switch), the drug is well tolerated, and there is no exclusionary drug interaction.

Fish oil and other omega-3 compounds must also be stable for  $\geq 3$  months at screening if the dose is  $\geq 1000$  mg per day.

Throughout study treatment, laboratory alerts will be in place to notify the Investigator of low-density lipoprotein-cholesterol (LDL-C) values. If LDL-C increases from baseline by 10 mg/dL and is >ULN on 2 consecutive visits, additional treatment (eg, initiation of statin therapy or an increase in the statin dose for patients who are already on treatment) may be introduced according to the 2018 AHA/American College of Cardiology (ACC) Guideline on the Management of Blood Cholesterol, after discussion with the Sponsor's Medical Monitor.

Throughout the study, it is recommended that a patient's LDL-C is managed in accordance with the 2018 AHA/ACC Guideline on the Management of Blood Cholesterol. The 2018 AHA/ACC Guideline on the Management of Blood Cholesterol recommends personalized risk assessments and new cholesterol-lowering drug options for people at the highest risk for cardiovascular disease. The guideline provides treatment algorithms for Primary Atherosclerotic Cardiovascular Disease (ASCVD) prevention and Secondary ASCVD prevention. See Appendix F for links to the full and abbreviated versions of the 2018 AHA/ACC Guideline on the Management of Blood Cholesterol.

In this study, it is recommended that a patient's LDL-C is managed with a statin, when necessary, in accordance with the treatment algorithm outlined in the 2018 AHA/ACC Guideline on the Management of Blood Cholesterol. In addition, Investigators should identify patients who are at "Very High Risk of Future ASCVD Events" who may benefit from additional LDL-C lowering therapy. Patients with "Very High Risk of Future ASCVD Events" include those with multiple major ASCVD events in the past or 1 major ASCVD event and multiple high-risk conditions as defined below:

- Major ASCVD events include the following:

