3.3.6 Prior and Concomitant Medications

Prior and concomitant medications will be coded to World Health Organization (WHO) Drug Dictionary Global B3, March 2019. Prior medications include any medication taken within 6 months prior to screening. Concomitant medications include any medication taken on or after the date the patient signs informed consent.

Counts and percentages of patients taking prior and concomitant medications by Anatomical Therapeutic Chemical (ATC) class and preferred term will be summarized by treatment group and overall for the Safety Population.

All medications will be listed and flagged as either prior or concomitant (or both).

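### SAP 3.6.2 summarises LDL-C as observed, with no account of the lipid-lowering treatment that a rise can itself trigger, so later visits can understate a rise

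*SAP*

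**What the plan says.** Protocol 5.6.2 states that during treatment "laboratory alerts will be in place to notify the Investigator of low-density lipoprotein-cholesterol (LDL-C) values". It then gives a criterion and a response: "If LDL-C increases from baseline by 10 mg/dL and is >ULN on 2 consecutive visits, additional treatment" may be introduced after discussion with the medical monitor. Its example is "initiation of statin therapy or an increase in the statin dose for patients who are already on treatment". Later paragraphs name ezetimibe and PCSK9 inhibitors as further options and recommend guideline-based LDL-C management throughout. Background therapy is allowed at entry: "Patients receiving lipid-lowering treatments need to be on stable therapy for at least 3 months prior to screening".

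No lipid variable is an efficacy endpoint in SAP 2.3.1 to 2.3.3, so LDL-C measurements are analysed through SAP 3.6.2: "Descriptive statistics of each clinical laboratory parameter will be presented for baseline values and for values and the change and percent change". That section also plans High/Low counts by visit, shift tables against extreme values, and listings. SAP 3.1.6 uses safety data as available. Neither section says how to treat values taken after a lipid-lowering drug is added.

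SAP 3.3.6 tabulates medications by class, preferred term and arm, under this definition: "Concomitant medications include any medication taken on or after the date the patient signs informed consent". The listing flags each drug as prior, concomitant or both.

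**The concern.** The added treatment is a consequence of the outcome being summarised. An arm with more LDL-C rises will tend to receive more lipid-lowering drug, and its later values then fall because of that drug. The later by-visit mean difference and the percentage High are pulled toward no effect, and the pull is stronger the larger the true rise. A reader of the Week 52 row would see LDL-C as managed, with nothing beside it showing how much management was needed in each arm.

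The two numbers that would show this are missing from the planned tables: how many patients per arm met the Protocol 5.6.2 criterion, and how many started or intensified treatment. Protocol 1.1 itself notes the strong association of NASH with cardiovascular disease, so the LDL-C result will be read closely.

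**Working it through.** **Inputs from the documents.** The criterion is in Protocol 5.6.2. Post-baseline treatment visits fall at Weeks 4, 10, 16, 24, 32, 40 and 52, with a lipid panel at each (Protocol Appendix A). The only LDL-C result is the interim row in Protocol 1.4.1.2, "LDL-C (mg/dL) 5.5 -3.9". These are placebo-adjusted changes at 300 mg and 600 mg, neither flagged as significant. The plan contains no figure for LDL-C variability, ULN, baseline level or treatment uptake, so there is nothing to reproduce and the size below rests on assumptions.

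**Step 1: when the effect can begin.** The criterion needs two consecutive post-baseline visits. The earliest pair is Weeks 4 and 10, so Week 16 is the first scheduled visit that criterion-based treatment can affect. Guideline-based treatment could start sooner.

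**Step 2: simple algebra.** If the average fall on added treatment is the same in both arms:

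observed difference = true difference − (excess share treated × fall on treatment)

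Take a true difference of 5.5 mg/dL, used only as an illustration, and a fall of 30 to 50 mg/dL:

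- 5% excess: 5.5 − 0.05×30 = 4.0, to 5.5 − 0.05×50 = 3.0
- 10% excess: 5.5 − 0.10×30 = 2.5, to 5.5 − 0.10×50 = 0.5
- 20% excess: 5.5 − 0.20×30 = −0.5, to 5.5 − 0.20×50 = −4.5

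**Step 3: simulation of the criterion.** Assumed inputs: baseline mean 105, between-patient SD 30, within-patient SD 15 and ULN 130 mg/dL; a 30% or 50% fall on treatment; 50% or 100% uptake at each qualifying visit; 200,000 patients per arm. Both parts of the criterion had to hold at both visits. Each range covers the four settings.

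| True rise (mg/dL) | Observed Week 52 difference (mg/dL) | Excess starting treatment (points) | Excess High at Week 52 if none treated (points) | Excess High as observed (points) | Excess normal-to-high at maximum (points) |
|---|---|---|---|---|---|
| 5.5 | 1.0 to 3.4 | 4.9 to 6.6 | 5.1 to 5.3 | 0.5 to 2.2 | 7.7 to 8.1 |
| 10 | 0.8 to 5.7 | 10.3 to 13.3 | 9.8 to 10.0 | 0.4 to 3.4 | 14.8 to 15.3 |
| 15 | −0.4 to 7.7 | 17.4 to 21.7 | 15.3 to 15.7 | −0.7 to 4.4 | 22.6 to 23.1 |

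The third column is active minus placebo: for a rise of 5.5 with full uptake and a 30% fall, 18.7% − 12.1% = 6.6 points. The last column is the same with and without added treatment, because a value above ULN must occur before the criterion is met.

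**Step 4: a second set of assumptions.** Mean 105 or 120, SDs 32 and 12, ULN 130, a 30% to 40% fall, and half or all of the patients meeting the criterion treated. A true 5.5 is observed as about 2.5 to 4.1 (half) or −0.4 to 2.6 (all). A true 15 is observed as about 5.5 to 9.9 (half) or −4.0 to 4.8 (all). With a rise of 15, mean 105 and all treated, 14% to 16% on drug against 17% on placebo are High at Week 52, although about 34% against 10% met the criterion. Roughly 40% to 55% of the active-arm patients meeting it were already High at baseline (36% to 48% with SDs 30 and 15), and the shift table shows no change for them.

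**The case against.** A reader might infer that the protocol expects LDL-C to rise, or that the drug raises it. The documents do not support that. The criterion is conditional. Protocol 5.2 says the 300 mg dose "demonstrated significant reductions in triglycerides and cholesterol, although not as notable as the effects seen with 600 mg dosing". The interim LDL-C difference was negative at 600 mg, the dose tested first.

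A reader might also infer that the SAP reports nothing but observed means and so hides any harm. That is too strong, because several planned outputs keep part of the signal:

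- Weeks 4 and 10 precede criterion-based treatment.
- The baseline-versus-maximum shift keeps the peak for patients normal at baseline.
- Protocol 8.1 makes a laboratory abnormality that requires intervention a reportable adverse event, and SAP 3.6.1 tabulates these by arm.
- A drug started on study carries only the concomitant flag in the listing, and randomisation should balance background use, so an excess in the class table is informative.

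All of this stands, but each item has a limit. The shift table counts any single high value rather than the sustained event, and its text names a maximum-baseline value where maximum post-baseline is evidently meant. Adverse-event reporting depends on intervention being required or on the investigator's judgement, whereas treatment under 5.6.2 is optional; LDL-C is not an event of special interest. The class table mixes entry statins with new ones and cannot show dose increases. Listings are not by-arm summaries.

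Observed values are also a legitimate description of LDL-C under the regimen as managed, and should stay.

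**Conclusion.** The point holds as a gap in safety reporting with a known direction. From about Week 16, the by-visit mean change and percentage High can understate an LDL-C rise in the arm with more rises, and no planned table gives the sustained event or treatment intensification by arm.

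The size is conditional on assumed LDL-C levels, variability, ULN, uptake and drug effect. A true 5.5 mg/dL keeps its sign at about 1.0 to 3.4 under one set of inputs, and ranges from −0.4 to 4.1 under the other. Loss or reversal of sign needs heavy uptake together with a strong fall on treatment. Nothing here shows that either dose raises LDL-C. The additions are worth making because they are cheap and address a directional bias; they do not affect the efficacy conclusions.

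**What to change.** In SAP 3.6.2 add three outputs by arm for the Safety Population:

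- **(a)** Number and percentage of patients meeting the Protocol 5.6.2 LDL-C criterion. State whether the 10 mg/dL rise must be present at both visits, in line with the protocol's intended reading.
- **(b)** Number and percentage starting or intensifying any lipid-lowering drug after the first dose, from the dated eCRF medication records.
- **(c)** A supportive summary of change in LDL-C and apolipoprotein B, either limited to values before such a start or increase or with the last prior value carried forward, placed beside the planned observed-value table. Say which is used.

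Label (c) a sensitivity summary, not an upper bound. Carrying forward values selected for being high can overstate the rise, more so in the arm with more events. Dropping later values instead removes those patients from later visits and can err the other way.

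Also correct the shift-table wording to maximum post-baseline.

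The cost is SAP text and three tables. LDL-C is measured at every visit and Protocol 5.6.3 already captures changes in concomitant dosing. No change to the treatment rule or to patient care is implied.
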